**Table 3: Clinical and non-clinical known risks and mitigation features**

Target System	Effect	Risk Mitigation
Renal System	
PQP: hepatorenal function and urinalysis did not change in study of PQP administration (500mg single dose in healthy adults) [25]. No trials have been conducted with Eurartesim® or PQP alone in patients with renal impairment.
	
 
1) Standard monitoring as with all early phase studies.
 
2) Urinalysis and safety bloods including urea, creatinine and glomerular filtration rate will be taken at regular intervals highlighted in the Schedule of Assessments (Table 5 and Table 6).
 
3) Additional assessments may be completed if required (including renal ultrasound, unscheduled microscopy or 24-hour urine collection).
 

	
PYR: Contraindicated in Severe renal failure.
 
Blood, protein or white cells in the urine have been seen uncommonly with Pyramax®.
 
Pre-clinical study in rats:
 
Pyronaridine decreased urine volume with a concomitant increase in density and electrolyte concentration at 500 mg/kg in the rat (no effect at 33 and 100 mg/kg). See Table 4-1 in PYR IB.
	
Hepatic System	
PQP: Overall considered as not commonly associated with LFT derangements [25]. LFT elevations have been seen uncommonly in healthy participants and malaria patients.
	
 
1) Specific Inclusion and Exclusion Criteria will be used to select potential participants (Sections 5.3 and 5.4).
 
2) Extensive liver function testing will be completed including ALP, AST, ALT, bilirubin, GGT, Total protein as well as Albumin and Globulin, and Coagulation will be measured as per the clinical Schedule of Assessments (Table 5).
 
3) Previous exposure to Hepatitis B (+/- D) and C will be assessed (excluding participants who have previous exposure).
 
4) Specific AR rules will be implemented.
 
5) Additional assessments could be added depending on clinical requirements, including a FibroScan of the liver.
 

	
PYR: is associated with transient asymptomatic increases in liver enzymes without bilirubin elevation in both healthy participants and patients [8].
 
Please see Risk Section 1.2.2.2 above for further details.
	

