**Table 5: Schedule of Assessments**

Procedure	Screening (D-22 to D-2)	D-1	D1	D2	D3	D4	D5	D6	D7  Sentinel Group only	D8	D15	D22	Last visit D30 (±1)	
In-house stay		X	X	X	X	X	X 	X	X					
Outpatient visit								X		X	X	X	X	
Informed consent	X													
Eligibility check	X	X												
Medical history/ demographics	X	X 												
Prior & concomitant medications	X	X	X	X	X	X	X	X	X	X	X	X	X	
Smoking history and current	X													
Beck depression inventory questionnaire	X													
Urine drugs of abuse screen	X	X												
Alcohol breath test	X	X												
Serology HIV 1&2, Hepatitis B&C	X													
Serum pregnancy test (females)	X	X											X	
FSH (post- menopausal females)	X													
Randomisation			X											
Trial drug administration 			X	X	X									
Meals 		X	X	X	X	X	X	X	X	X				
Safety and tolerability:														
Vital signs 	X	X	X	X	X	X	X	X	X	X	X	X	X	
12-lead ECG 	X	X	X	X	X	X	X	X	X	X	X	X	X	
24-hour Holter ECG	X													
Telemetry 			X	X	X									
BMI calculation	X	X 												
Physical examination 	X	X	X	X	X	X	X	X	X	X			X	

Procedure	Screening (D-22 to D-2)	D-1	D1	D2	D3	D4	D5	D6	D7  Sentinel Group only	D8	D15	D22	Last visit D30 (±1)	
Biochemistry, Haematology, Coagulation 	X	X	X	X 	X 	X	X	X	X	X	X	X	X	
Urinalysis	X	X	X		X		X		X	X	X	X	X	
Pharmacokinetics:														
PK sampling – PYR 			X	X	X	X		X		X	X	X		
PK sampling – PQP  (including e.g. N- oxidated metabolite)			X	X	X	X		X		X	X	X		
Pharmacogenomics:														
CYP polymorphism				X										

1. Vital signs (supine blood pressure, heart rate and respiratory rate) will be measured after rest of at least five minutes in supine position. Tympanic body temperature will be taken at each time-point (resting in supine position is not required for body temperature). Standing blood pressure and heart rate will be performed one minute after standing to assess for orthostatic change at screening and on Day -1, Day 1 and Day 3. See Table 6 for Time-points.
2. 12-lead ECG will be measured in triplicate after a rest period of at least ten minutes in supine position. See Table 6 for time-points.
3. Full physical examination at screening and last visit only. Symptom-directed physical examinations at other time-points.

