**Table 13: Laboratory parameters**

Haematology	Biochemistry	Urinalysis	

Platelets

Hb

Haematocrit

White blood cells

Neutrophils

Eosinophils

Basophils

Lymphocytes

Monocytes

Red blood cells

Mean cell haemoglobin (MCH)

Mean corpuscular haemoglobin concentration (MCHC)

Mean corpuscular volume (MCV)

HbA1c***

	

Aspartate aminotransferase (AST)

Alanine aminotransferase (ALT)

Alkaline phosphatase (ALP)

BUN

Gamma GT

Total bilirubin

Direct bilirubin

Indirect bilirubin

Creatinine

Urea

Total Serum Proteins

Albumin

Alpha1 Glycoprotein#

Sodium

Potassium

Calcium

Corrected calcium

Magnesium

Chloride

Bicarbonate

Amylase

Total cholesterol

Triglycerides

Serum pregnancy test*

FSH*

	

Leukocytes

Nitrite

Urobilinogen

Protein

pH

Blood

Specific gravity

Ketones

Bilirubin

Glucose

Urine microscopy**

	
Coagulation			

aPTT

PT

Fibrinogen

INR

	

Amylase

	Urine Screen for Drugs of Abuse	
Serology			

Hepatitis B surface Antigen (HBsAg)

Hepatitis B core Antibody (anti-HBC IgG + IgM, if IgG positive)

Hepatitis C Antibody (anti-HCV)

HIV I and II Antibodies

	

Total cholesterol

Triglycerides

Serum pregnancy test*

FSH*

	

Benzodiazepines

Opiates

Amphetamines

Methamphetamines

Methadone

Cocaine

Cannabinoids

Barbiturates

Phencyclidine

Tricyclic antidepressants

	

\* Measured at the times presented in the Schedule of Assessments (Table 5 and Table 6). Serum pregnancy test for pre-menopausal women only; FSH for post-menopausal women only. \*\* Only if urinalysis is abnormal. \*\*\* Measured at screening only. # On admission day only.

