### **7.6.4 Urinalysis**

Urine samples for determination of urinalysis parameters will be taken at the times given in the Schedule of Assessments (Table 5 and Table 6). If deemed necessary, based on a clinically significant positive test, microscopic examination of urine will be performed.

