### 8.1 Definitions

An '**Adverse Event (AE)**' is any unfavourable and unintended sign (including an abnormal laboratory finding), symptom or disease temporally associated with the use of a medicinal product, whether considered related to it or not.

An AE may be:

- a new symptom or medical condition
- a new diagnosis
- an inter-current illness or an accident
- a worsening of a medical condition/disease(s) that existed before the start of the clinical trial
- the recurrence of a disease
- an increase in frequency or intensity of episodic diseases
- a change in a laboratory or other clinical test parameter
  - the criteria to determine whether an abnormal test result should be reported as an AE/AR are as follows. The abnormal test result:
    - is associated with accompanying symptoms, and/or
    - requires additional diagnostic testing or medical/surgical intervention
- an event that leads to a change in trial dosing outside of protocol-stipulated dose adjustments, or discontinuation from the trial, significant additional concomitant drug treatment, or other therapy, and/or

- considered an Adverse Event by the Investigator or Sponsor.

An AE does not necessarily include the following:

- an abnormal test that needs repeating, in the absence of any of the above conditions. Any abnormal test result that is determined to be an error does not require reporting as an Adverse Event
- surgical procedures themselves are not AEs; they are therapeutic measures for conditions that require surgery. The condition for which the surgery is required may be an AE/AR. Planned surgical measures permitted by the clinical trial protocol and the condition(s) leading to these measures are not AEs, if the condition leading to the measure was present before inclusion in the trial and has not worsened. In the latter case, the condition should be reported as medical history.

A '**Serious Adverse Event (SAE)**' is defined as any Adverse Event that fulfils any of the following criteria:

- it results in death
- it is life-threatening (the term 'life-threatening' in the definition of 'serious' refers to an event in which the participant was at immediate risk of death at the time of the event; it does not refer to an event which hypothetically might have caused death if it were more severe)
- it requires a hospitalisation\* or prolongs existing hospitalisation
- it results in persistent or significant disability/incapacity
- it is a congenital abnormality/birth defect

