### 2.2 Endpoints

#### Primary

- The incidence, severity and relationship of Treatment-Emergent Adverse Events (TEAEs).
- Proportion of participants with clinically significant changes in laboratory safety tests (haematology, biochemistry, coagulation and urinalysis).

- Proportion of participants with morphological and/or rhythm abnormalities on electrocardiogram (ECG).
- Proportion of participants with clinically significant changes in ECG time intervals (PR, QRS, QT and QTc intervals) and clinically significant changes against baseline Holter.
- Proportion of participants with clinically significant changes in vital signs (systolic blood pressure, diastolic blood pressure and pulse rate).

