### 4.11.2 Laboratory Data

Clinical laboratory parameters (including blood chemistry, haematology, coagulation, urinalysis and other laboratory results) will be listed and abnormal parameters will be flagged and graded as high (H/x) or low (L/x) (where defined) according to reference ranges and CTCAE grade. Absolute (observed) values and changes from baseline (continuous variables) will be summarized for each parameter and scheduled time point by treatment group. The number of volunteers presenting out-of-range and clinically relevant values will be summarised by treatment group. The scheduled lab value will be used for summary analysis if repeated measurements are made at any time point.

For summary statistics, a lab value with "<" will be replaced with a numeric value by removing the "<" sign. In the listings, the values will be displayed as originally reported by the laboratory.

The mean and individual change from baseline value of ALT/AST/Bilirubin will be plotted by treatment group and by time-point. The number of subjects presenting out-of-range and clinically relevant values will be summarised.

The qualitative urinalysis data will be listed only.

Test Code	Test Unit	Range Low	Range High	Grade 1	Grade 2	Grade 3	Grade 4
ALT	IU/L	10	50	>ULN - 3.0 x ULN	>3.0 - 5.0 x ULN	>5.0 - 20.0 x ULN	>20.0 x ULN

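### Urinalysis is part of a primary endpoint defined as a proportion, but qualitative urine results are planned for listing only

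*SAP*

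**What the plan says.** **Endpoint.** SAP 2.2 defines the second primary endpoint as: "Proportion of participants with clinically significant changes in laboratory safety tests (haematology, biochemistry, coagulation and urinalysis". Protocol 2.2.1 has the same definition.

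**Analysis.** SAP 4.11.2 opens by including urinalysis among the clinical laboratory parameters. It then says: "The number of volunteers presenting out-of-range and clinically relevant values will be summarised by treatment group". Its text ends with: "The qualitative urinalysis data will be listed only". Protocol 10.3 also promises counts of out-of-range and clinically relevant laboratory values and makes the same exemption for qualitative urinalysis.

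**Panel.** The urinalysis column of protocol Table 13 begins "Leukocytes Nitrite Urobilinogen Protein" and continues with pH, blood, specific gravity, ketones, bilirubin and glucose. Microscopy is added only when the result is abnormal. The table does not say which items are reported as categories.

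**Schedule.** The row in protocol Table 5 reads "Urinalysis X X X X X X X X X X". The ten marks fall at screening and on Days -1, 1, 3, 5, 7, 8, 15, 22 and 30. The Day 7 column is headed as sentinel group only.

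**Stated risk.** The renal row of protocol Table 3 says, under PYR: "Blood, protein or white cells in the urine have been seen uncommonly with Pyramax". It names urinalysis as part of the mitigation.

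**The concern.** The endpoint asks for a proportion of participants, and a listing does not report one. A programmer who follows the specific sentence in SAP 4.11.2 will leave qualitative urine results out of the by-arm counts that the same section promises for laboratory data. One of the four laboratory components of a primary endpoint would then be only partly reported.

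The primary objective is to describe safety alone and in combination, in comparison with placebo. For qualitative urine findings the report would contain no table setting the combination beside PYR alone, PQP alone and placebo. Blood, protein and leukocytes, the urinary findings that the protocol itself singles out, are probably among the items affected.

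**Working it through.** The point rests on text. The only arithmetic concerns the schedule and the likely number of events.

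**1. The rules side by side**

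| Place | What it requires for qualitative urine results |
|---|---|
| Protocol 2.2.1, SAP 2.2 | A proportion of participants |
| SAP 4.11.2, general sentence | A count by treatment group |
| SAP 4.1, default for categorical variables | Frequencies and percentages |
| SAP 4.11.2 and protocol 10.3, specific sentence | A listing and nothing more |

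The first three rows agree and the fourth contradicts them. A specific rule normally overrides a general one, so the natural reading is that no count is produced.

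**2. Which items are affected**

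Table 13 has ten routine urinalysis items. If dipstick items are reported as categories in the usual way, eight are qualitative: leukocytes, nitrite, urobilinogen, protein, blood, ketones, bilirubin and glucose. The other two, pH and specific gravity, are numeric and stay under the general rule. The 8-to-2 split is an assumption, because the documents do not classify the items.

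**3. Whether the data exist**

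- Marks in Table 5: 10. Less screening and Day -1: 10 − 2 = 8 on or after Day 1.
- Table 6 gives no urine time on Day 1, so that sample may be pre-dose. Clearly post-dose: 8 − 1 = 7 (Days 3, 5, 7, 8, 15, 22, 30).
- Without the sentinel-only Day 7: 7 − 1 = 6.

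The schedule therefore gives 7 clearly post-dose samples in the sentinel group and 6 in the main group, or 8 and 7 if the Day 1 sample follows dosing. All four arms share this schedule. The SAP's flow-chart note says that both groups stayed in-house until Day 7, but does not say whether the main group gave urine that day.

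**4. How many events to expect**

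The plan's only numerical planning figure is the chance of at least one event among 16 participants, 1 − (1 − p)^n:

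- p = 10%: 1 − 0.9^16 = 81.5% (stated 81%)
- p = 20%: 1 − 0.8^16 = 97.2% (stated 97%)

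Both reproduce. Table 3 gives no rate for the urinary findings. For another uncommon PYR effect it gives 1/1000 to 1/100. Taking that band as an assumption:

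- 24 planned PYR-exposed participants (16 + 8): 1 − 0.999^24 = 2.4% to 1 − 0.99^24 = 21.4%
- 8 on PYR alone: 1 − 0.999^8 = 0.8% to 1 − 0.99^8 = 7.7%

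SAP 3.2 says recruitment stopped at 37, so actual arm sizes, and with them these chances, may be lower.

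**The case against.** **The findings will appear as adverse events.** Protocol 7.6.4 provides, if deemed necessary, that "based on a clinically significant positive test, microscopic examination of urine will be performed". Protocol 8.1 treats an abnormal test as an adverse event when it has symptoms or "requires additional diagnostic testing or medical/surgical intervention". Treatment-emergent events are tabulated by arm. This route is real but partial. It is a separate primary endpoint, microscopy is discretionary, and protocol 8.3 discourages recording as an adverse event a sign already captured by another protocol method, apart from stated exceptions. An asymptomatic dipstick change could be missed.

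**Counts can be made by hand.** SAP 4.1 orders listings by treatment group, and there are 37 participants. This stands: the data are not lost and a reader could count them. What is missing is the reported endpoint result.

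**The exemption may cover only means and standard deviations.** In protocol 10.3 the sentence directly follows the description of those statistics for quantitative data, which gives this reading some support. In SAP 4.11.2, however, it directly follows a sentence about counts, and its wording excludes anything beyond a listing. At best the section is ambiguous and still needs reconciling.

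**The table would be mostly zeros.** Probably so, in an exploratory trial with descriptive safety analysis. That limits the weight of the point. In a first study of a combination, though, a tabulated zero per arm is a result.

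**Conclusion.** The conflict holds: both documents name urinalysis in a primary endpoint that is a proportion, and both then confine qualitative urinalysis to a listing. The impact is modest. No hypothesis test or sample-size statement depends on it, and some findings would still be tabulated as adverse events.

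The conclusion assumes conventional dipstick reporting. It also assumes that clinically relevant in the analysis text means the same as clinically significant in the endpoint. The table shells are not among the documents, so a table planned there would not be visible.

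Four stronger readings are not supported:

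- *PYR causes these urinary findings.* Table 3 says only that they were seen uncommonly with Pyramax, which combines PYR with artesunate. It makes no causal statement.
- *The whole urinalysis component is dropped.* Only qualitative results are exempted. Numeric ones remain under the general rule.
- *The arms cannot be compared.* They can, by hand, from the listings.
- *The SAP departs from the protocol.* The two agree. The mismatch is between endpoint and analysis in each.

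**What to change.** In SAP 4.11.2 and protocol 10.3, replace the listing-only sentence with wording such as: *Qualitative urinalysis data will be listed, and the number and percentage of participants per treatment arm with at least one post-dose urinalysis result flagged clinically significant will be summarised, overall and by parameter.*

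Use the clinical-relevance flag that protocol 10.3 already applies to laboratory values, and state that it is also set for qualitative results. State whether the Day 1 sample is pre-dose or post-dose. No new threshold is needed: a rule counting any shift from negative or trace to positive has no basis in the documents, and would count changes that are not clinically significant.

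The cost is one descriptive table from results already scheduled for collection, probably with few events.

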# Statistical Analysis Plan

AST	IU/L	0	37	>ULN - 3.0 x ULN	>3.0 - 5.0 x ULN	>5.0 - 20.0 x ULN	>20.0 x ULN
Total bilirubin	UMOL/L	0	20	>ULN - 1.5 x ULN	>1.5 - 3.0 x ULN	>3.0 - 10.0 x ULN	>10.0 x ULN

## 4.11.3 Vital Signs

Vital signs data (SBP, DBP, Pulse rate, temperature) will be listed for individual subjects. Summary statistics of absolute (observed) values and changes from baseline will be calculated for each parameter and scheduled timepoint by treatment group.

Out-of-reference-range values will be flagged as high (H) or low (L) and as being clinically relevant or not: the number of subjects presenting out-of-range and clinically relevant values will be summarised.

Parameter	Normal Range
Temperature (tympanic)	35-37.5°C
Systolic Blood Pressure (Supine)	90-140 mmHg
Diastolic Blood Pressure (Supine)	40-90 mmHg
Postural Drop (systolic, symptomatic)	≤20 mmHg drop
Pulse Rate (supine)	40-100 bpm
Respiratory Rate	8-20 breaths per min

## 4.11.4 Telemetry and Holter

Cardiac telemetry and Holter data (Start / End Date time and evaluation) will be listed by subject.

## 4.11.5 Physical Examination

The physical examination performed at screening and at the post-trial visit will be listed only and include an assessment of the following: general appearance, skin, eyes/ears/nose, neck, lymph nodes, throat, heart, lungs, abdomen, musculoskeletal system and extremities.

## 4.11.6 Electrocardiograms

ECG analyses will be performed on two sets of ECGs: all ECGs prior to adjudication by a cardiologist and selected triplicates from each time-point after adjudication. The latter analyses will be performed as contracted.

# Statistical Analysis Plan

All un-adjudicated ECG data (PR, QRS, QT, QTcB, QTcF and HR) including H/L flags and overall ECG evaluation will be listed. Out-of-reference-range values will be flagged as clinically relevant or not. Reference ranges for ECGs are as follows:

Parameter	Normal Range
Heart Rate (Supine)	40-100 bpm
PR Interval	120-220 ms
QRS duration	≤120 ms
QTcF	≤450 ms (Males & Females)

For summary statistics an arithmetic mean value, of the last 3 evaluable ECGs of each timepoint, will be used at each time-point. All below analyses will be performed using this set.

ECG data and changes from baseline will be summarised using descriptive statistics.

The change from baseline will be derived using the arithmetic mean value of each time-point triplicate minus baseline value, where baseline is the arithmetic mean of the pre-dose QTcF values of Day 1.

Furthermore, categorical analysis of QTcF data will be presented as follows:

- Absolute QTcF interval prolongation
  - QTcF interval > 450 ms to ≤ 480 ms
  - QTcF interval > 480 ms to ≤ 500 ms
  - QTcF interval > 500 ms
- Change from baseline in QTcF interval
  - QTcF interval increases from baseline > 30 msec to ≤ 60 msec
  - QTcF interval increases from baseline > 60 ms

The mean change from baseline value of QTcF will be plotted by treatment group and by time-point. The number of subjects presenting out-of-range and clinically relevant values will be summarised.

Additional categorical analysis will be presented as follows:

- increase of PR from baseline >25% resulting in PR > 200 ms
- increase of QRS from baseline >25% resulting in QRS > 120 ms
- decrease of HR from baseline >25% resulting in HR < 50 bpm
- increase of HR from baseline >25% resulting in HR > 100 bpm.

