### **7.9 Electrocardiographic (ECG) measurements**

#### **7.9.1 Recording of 12-lead ECGs**

12-lead ECGs will be recorded at the time-points described in the Schedule of Assessments (Table 5 and Table 6) using a GE ECG recorder connected via a fixed network connection to the MUSE® Cardiology Information System (MUSE®). ECGs recorded during screening will be stored electronically on the MUSE® information system. Only ECG recorded electronically will be valid ECG for any purpose other than safety assessment. ECG printouts may be filed in the participant's CRF for medical safety reviews.

Each ECG recorder will be set up to the required technical specifications and will contain the information required to identify the records. Each ECG recording will be clearly identified (with participant ID, visit date, and the actual times of ECG recordings).

12-lead ECG recordings will be made after the participants have been resting in a supine position for at least ten minutes. The participants will avoid postural changes during the ECG recordings and clinical staff will ensure that participants are awake during the ECG recording.

At each time point, the ECG will be recorded in triplicate, to reduce variance and to improve the precision of measurement. The triplicates will be performed at approximately one-minute intervals. Each ECG recording (trace) will last ten seconds. Repeat ECG will be performed until at least three ten-second ECG records per scheduled time-point meet the quality criteria set out in the SOM and the

---

applicable SOP to enable the reading and analysing of at least five complexes per derivation.

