### **7.9.2 Safety review of 12-lead ECGs**

All recorded ECGs will be reviewed by an RP and the review will be documented in the CRF. If a participant shows an abnormal ECG, additional safety recordings (including the use of 5-lead or 12-lead Holter equipment) may be made and the abnormality be followed to resolution if required.

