Page layout of the TFLs will be in landscape mode and will be provided as individual RTF format. Further details of page layout will be provided in the TFL shell document.

If repeated measurements are made at a time point, the first scheduled value will be used for summary analysis, unless otherwise stated in relevant section of this SAP.

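### The un-adjudicated ECG tables use the last three evaluable ECGs per timepoint, so if repeats prompted by an abnormal ECG are coded to that timepoint, the abnormal triplicate drops out of the outlier counts

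*SAP*

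**What the plan says.** SAP 4.11.6 (un-adjudicated ECGs) states: "For summary statistics an arithmetic mean value, of the last 3 evaluable ECGs of each timepoint, will be used at each time-point". It then adds: "All below analyses will be performed using this set". What follows in that section includes the change from baseline, the absolute QTcF categories beginning with "QTcF interval > 450 ms to ≤ 480 ms", the change-from-baseline QTcF categories, the counts of out-of-range values, and the PR, QRS and heart-rate categories.

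Elsewhere the SAP keeps the original value. The default in SAP 4.1 is "If repeated measurements are made at a time point, the first scheduled value will be used for summary analysis", unless a section says otherwise, and 4.11.6 does. For laboratory data, SAP 4.11.2 says: "The scheduled lab value will be used for summary analysis if repeated measurements are made at any time point". SAP 4.1 also limits summary tables to observed values from scheduled timepoints.

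The protocol gives two reasons why more than three traces may exist at a timepoint:

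- **Quality (7.9.1):** "Repeat ECG will be performed until at least three ten-second ECG records per scheduled time-point meet the quality criteria".
- **An abnormal result (7.9.2):** "If a participant shows an abnormal ECG, additional safety recordings (including the use of 5-lead or 12-lead Holter equipment) may be made".

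**The concern.** If repeats stop once three good traces exist, the last three evaluable ECGs are the three good ones and the rule is harmless. The word *last* matters when further evaluable ECGs follow a complete triplicate, and an abnormal reading is one documented reason for that. The rule then keeps the later recordings and drops the ones that raised the concern, so whether a value is counted depends on the value itself. For QTcF the SAP reference range has only an upper limit (450 ms), so replacement prompted by that range works in one direction.

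What is at stake is the un-adjudicated outlier tables. Changes in ECG intervals belong to the primary safety endpoints, and Protocol section 1 names QTc prolongation as one of three toxicities of focus, expected mainly with PQP. Readings above the limit, and so any replacements, would be expected mostly in the PQP arms. Arms have 8 or 16 planned participants, so one participant moved out of a category is visible.

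**Working it through.** **The plan's own figure.** The only design figure stated is the chance of at least one event among 16 combination participants: 1 − 0.9^16 = 81.5% (stated 81%) and 1 − 0.8^16 = 97.2% (stated 97%). Both reproduce. The ECG rule has no stated figure.

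**Model 1: one timepoint.** The inputs are assumptions, apart from the 450 ms limit in SAP 4.11.6. True QTcF is normal with mean 425 and SD 17 ms. The triplicate mean has error SD e = 4 to 8 ms. A share r of triplicates above 450 ms is repeated once, the true value is unchanged, and the repeat replaces the first.

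- True proportion above 450: z = 25/17 = 1.47, giving 7.1%.
- First triplicate: F = P(Z > 25/√(17² + e²)).
- Last three: (1 − r)F + rB, where B is the probability that first and repeat both exceed 450, that is, P(error > 450 − t)² averaged over the true value t.
- Mean fall in a repeated value: (e²/s)·φ(z)/(1 − Φ(z)), with s = √(17² + e²) and z = 25/s. Multiplying by F gives the shift in the overall mean when r = 1.

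Worked case, e = 6: s = √325 = 18.03, z = 1.387, F = 8.28%, B = 5.44%. With r = 1 the count falls by 1 − 5.44/8.28 = 34%. With r = 0.5 the proportion is (8.28 + 5.44)/2 = 6.86%, which is 17% below the first-triplicate figure and 3% below the true 7.07%. Repeated values fall by (36/18.03) × 1.84 = 3.7 ms, and the overall mean by 3.7 × 0.0828 = 0.30 ms.

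| e (ms) | First vs true | Last three vs first, r = 1 | vs true, r = 1 | vs first, r = 0.5 | vs true, r = 0.5 | vs true, r = 0.25 | Fall in repeated values (ms) | Overall mean shift, r = 1 (ms) |
|---|---|---|---|---|---|---|---|---|
| 4 | +8% | −24% | −18% | −12% | −5% | +1% | 1.7 | 0.13 |
| 5 | +12% | −29% | −21% | −15% | −5% | +4% | 2.6 | 0.21 |
| 6 | +17% | −34% | −23% | −17% | −3% | +7% | 3.7 | 0.30 |
| 8 | +30% | −43% | −26% | −21% | +2% | +16% | 6.1 | 0.56 |

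**Model 2: participants over the whole schedule.** This is a simulation of 16 participants with 36 ECG timepoints after the first dose, counted from Protocol Tables 5 and 6: 9 on Day 1, 6 on Day 2, 13 on Day 3, and 8 on Days 4 to 8, 15, 22 and 30. Day 7 is included, although the protocol schedules it for the sentinel group only. Assumed inputs are mean QTcF 410 to 430 ms, between-participant SD 15, between-timepoint SD 8, single-trace SD 4 to 12 ms, and half or all of the triplicates above 450 ms repeated.

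- The last-three count of timepoints above 450 ms was 0.48 to 0.94 of the first-triplicate count.
- The count of participants with any such value was 0.52 to 0.96 of the first-triplicate count.
- Example (mean 420, trace SD 8): 4.1 of 16 participants with the first triplicate, against 3.0 with the last three if all are repeated, or 3.6 if half are.
- Repeats at a random 10% of timepoints left the counts unchanged, so the fall comes from replacing only high values.

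**The case against.** The strongest reply is that the documents do not show the replacement happening. Protocol 7.9.2 says only that extra recordings may be made. It mentions Holter equipment and follow-up to resolution, which need not mean a second triplicate at the same timepoint. SAP 4.1 restricts summary tables to scheduled timepoints, so a repeat coded as unscheduled is already excluded and the original stays. This stands: the point depends on coding that neither document settles. However, a rule that picks the last three at a timepoint presupposes that more than three can sit there.

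The rule also has a neutral use. A reader might assume that a trace failing quality is never evaluable, so that surplus evaluable ECGs must come mainly from abnormal results. The documents do not say so. SAP 4.11.6 does not define evaluable, and the ECG set in SAP 4.3 ties it to measurable QT and RR. A trace could meet that and still fail the site criteria in Protocol 7.9.1. Passing traces then tend to come last, and taking the last three is sensible. This also stands, and it is why simply changing *last* to *first* would be a poor fix.

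Finally, the first triplicate is not the truth. Measurement error inflates its count by 8% to 30% in Model 1, and at moderate repeat rates the last-three count can lie closer to the true one. That is so, but only through an unknown, discretionary repeat rate. The scheduled triplicate applies the same rule to every participant.

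**Conclusion.** The point holds conditionally. If repeats prompted by an abnormal ECG are coded to the scheduled timepoint, SAP 4.11.6 removes the triggering triplicate from the categorical tables. Counts above 450 ms, and those in the other categories where an abnormal reading prompted the repeat, are then lower than the scheduled triplicates would give. The size rests on assumed variances and an unknown repeat rate; repeats made only for quality cause no such loss.

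Three stronger readings are tempting but unsupported:

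- **Counts below the truth in every case.** Under Model 1 that is clear only when nearly all high triplicates are repeated. At half it is −5% to +2%, and at a quarter +1% to +16%.
- **A materially lower mean QTcF change.** Repeated values fall by 1.7 to 6.1 ms, but the overall mean moves by only 0.1 to 0.6 ms even if all are repeated.
- **A biased placebo-corrected QTc analysis.** That analysis is specified in SAP 4.12 on adjudicated ECGs, to which this rule does not apply.

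Nor are abnormal values lost altogether. All un-adjudicated ECGs are listed with flags, a physician reviews every recording, and clinical significance is a matter of judgement.

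**What to change.** In SAP 4.11.6:

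1. Summarise the mean of the first three ECGs at the scheduled timepoint that meet the Protocol 7.9.1 quality criteria. Quality-driven repeats then still replace poor traces.
2. State that recordings prompted by an abnormal result are coded as unscheduled, kept out of the timepoint summaries, and listed.
3. Add a worst post-dose value row, including unscheduled ECGs, to each categorical table.

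This brings the section into line with SAP 4.1 and 4.11.2 and needs no new data. The cost is one flag in the ECG dataset and one extra row per categorical table. The worst-value row will show somewhat higher outlier counts because of measurement error, and a footnote should say so.
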